1.3 Compliance Statement

This study will be conducted in full accordance with all applicable Children’s Hospital of Philadelphia Research Policies and Procedures and all applicable Federal and state laws and regulations including 45 CFR 46 and the Good Clinical Practice: Consolidated Guideline approved by the International Conference on Harmonization. All episodes of noncompliance will be documented.

The investigators will perform the study in accordance with this protocol, will obtain consent and assent, and will report unanticipated problems involving risks to subjects or others in accordance with Children’s Hospital of Philadelphia IRB Policies and Procedures and all federal requirements. Collection, recording, and reporting of data will be accurate and will ensure the privacy, health, and welfare of research subjects during and after the study.

2 STUDY OBJECTIVES

Our long-term goal is to test the effects of AH approaches to promote child language and socio-emotional development. As such, we will incorporate behavioral economic approaches using automated hovering (AH) to improve the frequency of parent-child shared reading in low-income children and help ameliorate disparities for school readiness.

2.1 Primary Objective (or Aim)

Specific Aim 1: To determine the feasibility and acceptability of automated hovering of varying intensity designed to improve the frequency of parent-child reading behaviors among low-income families.

2.2 Secondary Objectives (or Aim)

Specific Aim 2: To explore differences in reading frequency, the home reading environment, parenting stress, and child language and socio-emotional development by the intensity of the automated hovering strategy among low-income families.

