Early shared reading strategies, such as Reach Out and Read (ROR) and Imagination Library, promote parent-child shared reading and distribute board books to low-income children.^{8,14} These strategies have demonstrated greater interest in shared reading and improved child language development compared to usual care among poor children and their families. However despite these beneficial effects, low-income children and their families engaged in these programs have only shown modest improvements in the frequency of shared reading and still lag behind their higher income peers in language development.¹⁵

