3 INVESTIGATIONAL PLAN

3.1 General Schema of Study Design

To be eligible to participate, children must be aged 6-24 months old, and have a parent with daily access to a smart phone in order to receive and send text messages. Inclusion and exclusion criteria for Phase 1 will be the same as Phase 2. In our previous study utilizing text messaging with low-income families for a study of early literacy promotion, only 28 (18.9%) of 148 eligible participants approached for recruitment were ineligible because they didn't have access to a smart phone. Children and their parents will be recruited from participating practices at any 6 through 24-month well child visit in which parents receive board books and reading promotion from their child's clinician as part of the ROR program.

3.1.1 Phase 1

Prior to conducting the RCT, we will develop the text messages and personalized coaching that we will employ in the RCT. The text messages were previously developed as part of the aforementioned trial on early literacy promotion (see appendix). Using a rapid-cycle design process developed by [name], data from brief interviews with N=10 parents will be used to identify specific behavioral barriers to more frequent reading with children, and to edit reminder messages and develop coaching content to target those barriers with behaviorally-informed solutions. Personalized coaching will consist of a menu of various instruction and tips on reading that participants can select based on their needs. The interviews will be audio recorded and transcribed in order to analyze content. In the event that the baseline visit cannot be completed in-person, an alternative method of obtaining informed consent will be used, and the interview will be completed over the phone. All interviews will be audiotaped and transcribed for analysis. Interview transcripts will be analyzed and coded using NVivo, a qualitative software. The information can inform the motivational tips in phase 2 to address barriers to shared reading.

Following the telephone screening, caregivers of eligible children will be sent the informed consent document electronically through REDCap. The study team will then go over the document in detail with the eligible caregiver by phone and use the e-consent function to obtain their signature. The signed e-consent form will be stored within REDCap and a copy will be made available to download and email securely to the caregiver.

3.1.2 Phase 2

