After conducting the rapid-cycle design for phase 1, forty-five eligible children and their parents will be consented and enrolled in the study. In the event that the baseline visit cannot be completed in-person an alternative method of obtaining informed consent electronically through REDCap will be used. Following informed consent and completion of baseline surveys, participants will be stratified by site and randomized 1:1:1 to receive one of the 3 AH interventions for an 8-week duration. Using a similar recruitment strategy, we were able to successfully recruit 120 (81%) of 148 low-income infants and their parents who were approached for the aforementioned study on early literacy promotion.

Group 1 will consist of daily text messages on shared reading, which will be sent to participants using the Way to Health Platform. Participants will be asked to reply to the text message on daily shared reading activities including the titles of books and time spent reading. Group 2 will consist of Group 1 plus personalized coaching. Personalized coaching content will be made available to participants through links in the text messages and will provide comparisons of their reading frequency with that of other participants. These comparisons will be blinded to preserve confidentiality. Finally, Group 3 will consist of Group 2 plus availability of a weekly lottery. Group 3 participants who report back that they read on a particular day will be entered into a weekly drawing to receive \$20. Each reported daily reading behavior will provide a single lottery entry so that participants who report they read all 7 days in a given week will have 7 entries in the weekly drawing.

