3.4 Study Population

We plan to recruit 3-4 urban CHOP-affiliated pediatric practices from CHOP's Pediatric Research Consortium (PeRC) to participate in the study. These practices care for a diverse, complex urban population and have onsite social worker to assist with family crises. Using well-established methods that have proven effective in multiple large-scale trials, 3-4 practices located in Philadelphia will be recruited to participate using letters of invitation and in-person presentations. Incentives to participate will include provider education on parent-child shared reading. A total of 55 eligible children and their parents will be recruited from participating practices to achieve a diverse sample of children. Inclusion and exclusion criteria for Phase 1 will be the same as Phase 2. Children will be eligible to participate if they are 6-24 months old, and have a parent with daily access to a smart phone in order to receive and send text messages.

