5 STUDY EVALUATIONS AND MEASUREMENTS

5.1 Screening and Monitoring Evaluations and Measurements

5.1.1 Medical Record Review

Date of birth

Gestational age, sex, developmental assessments

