8.5 Recruitment Strategy

8.5.1 Subjects

Eligible children and their parents will be identified in the clinic by either research staff or clinic providers through the use of a recruitment flyer (see Appendix 8). The flyer will be used to deliver information of the study to eligible children and parents. If permitted, research staff will recruit in person at the clinic. Parents who verbally agree to be contacted will be asked to scan the QR code on the flyer to complete a REDCap referral form (see Appendix 9). The contact form will be stored within REDCap and will then be available for research staff to use. Medical records of the potentially eligible subjects will be screened and assessed for eligibility prior to contacting the subject. Subsequent to screening the medical record, the subject will be called by the research staff to explain the study and arrange for a study visit. Research staff will briefly explain the study procedures, guided by the information set forth in the approved consent form. This includes reading the inclusion criteria to the potential participant, and asking whether or not this individual is interested in participating. Research staff will then schedule a time to meet with the parent in person- or remotely to complete the baseline visit. At this visit, parents will be asked to provide written informed consent to participate in the study. In the event that the baseline visit cannot be completed in-person, an alternative method of obtaining informed consent will be used. Following the telephone screen, caregivers of eligible children will be sent the informed consent document electronically through REDCap. The study team will go over the document in detail with the eligible caregiver by phone. The e-consent function in REDCap will be used to obtain the caregiver's signature. The signed e-consent will then be stored within REDCap and a copy of the form will be available to download and emailed securely to the caregiver.

The rationale for the involvement of children in the study is that the investigation addresses child development in pediatric care settings. The study does not involve any other special class of subjects.

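### Does an aim about low-income families need an income criterion or a separate low-income outcome summary?

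*Combined protocol and SAP*

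**What the plan says.** **Aims.** Section 2.2 states Aim 2 as exploring differences "by the intensity of the automated hovering strategy among low-income families". Aim 1 (section 2.1) concerns the feasibility and acceptability of an intervention "designed to improve the frequency of parent-child reading behaviors among low-income families". There the phrase follows the behaviour to be improved, so it can describe what the intervention is for and not who is sampled.

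**Eligibility and screening.** Sections 3.1, 3.4, 3.4.1 and 3.4.2 cover the child's age, the parent's smart phone, consent, English, gestational age, and malformations or syndromes. None has an income term. The record review in section 5.1.1 lists date of birth and "Gestational age, sex, developmental assessments". Section 8.5.1 says "Medical records of the potentially eligible subjects will be screened and assessed for eligibility prior to contacting the subject" and adds a telephone call, again without an income check. Section 3.4 says that families "will be recruited from participating practices to achieve a diverse sample of children".

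**Setting.** Section 3.1 recruits "at any 6 through 24-month well child visit in which parents receive board books and reading promotion" through Reach Out and Read. Section 1 describes such programmes as ones that "promote parent-child shared reading and distribute board books to low-income children". Section 3.1.2 reports that with a similar recruitment strategy "we were able to successfully recruit 120 (81%) of 148 low-income infants and their parents".

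**Data and analysis.** Section 3.1.3 collects family income category at baseline. Section 5.1.2 assesses poverty from income below 100% of the Federal Poverty Level and maternal education of high school or less. Section 6.4.1 describes demographics by arm. Section 6.4.3 compares arms by intention to treat and has no outcome summary by income.

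**The concern.** An aim that names a population should be answered in that population. Here anyone attending a participating practice can enrol regardless of income, and the stated wish for diversity could be read as inviting higher-income families. The plan also defines a poverty indicator and then makes no use of it in the outcome section.

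If many enrolled families were not low-income, the feasibility, acceptability and reading-frequency results would describe a mixed group. The abstract intends the results to inform later grant applications in low-income children, and section 6.4.3 computes effect sizes to power future studies. A feasibility rate raised by better-off families could then be carried into planning for poorer ones. The remedy that suggests itself is an outcome table restricted to families below the poverty threshold, with a sentence limiting the conclusions.

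**Working it through.** **Inputs from the documents.** Phase 2 has 15 families in each of 3 arms (section 6.4.2): 3 x 15 = 45, which reproduces the stated target. The abstract also mentions 55 for Phase 2; that would alter the subset counts below but not the dilution figures. The earlier recruitment figure also reproduces: 120/148 = 81%. The documents give no low-income share, no share below the poverty threshold, and no power calculation.

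**Assumptions.** The shares, the gaps between income groups and the observed counts below are all illustrative.

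**Step 1: dilution.** If a share s of families belongs to the target group, and outcomes differ by a gap g between the target group and the rest, then

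all-families value - target-group value = (1 - s) x g.

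| Assumed share s | g = 10 points | g = 20 points |
|---|---|---|
| 40% | 6 | 12 |
| 60% | 4 | 8 |
| 80% | 2 | 4 |
| 90% | 1 | 2 |

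**Step 2: which share applies.** Aim 2 names low-income families. The indicator in section 5.1.2 is poverty, which may be narrower. Suppose 90% of families are low-income but only 40% fall below the threshold, and use the same gap for both splits:

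- All families against low-income families: 0.10 x 10 = 1 and 0.10 x 20 = 2 points.
- All families against families below the threshold: 0.60 x 10 = 6 and 0.60 x 20 = 12 points.
- Families below the threshold against low-income families: 6 - 1 = 5 and 12 - 2 = 10 points.

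In this example the planned all-families summary lies 1 to 2 points from Aim 2's population, and the poverty subset lies 5 to 10 points from it. The 6 to 12 points at a 40% share would be the error for Aim 2 only if low-income meant exactly below the threshold and only 40% of families were there.

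**Step 3: what the subset could show.** Subset size is 45 x share:

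- 40%: 18 families, 6 per arm.
- 60%: 27 families, 9 per arm.
- 80%: 36 families, 12 per arm.
- 90%: 40.5 families, 13.5 per arm.

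95% Wilson intervals for assumed counts near 80%:

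| Per arm | Interval | Pooled over arms | Interval |
|---|---|---|---|
| 5/6 | 44-97% | 14/18 | 55-91% |
| 7/9 | 45-94% | 21/27 | 59-89% |
| 10/12 | 55-95% | 29/36 | 65-90% |
| 12/15 (full arm) | 55-93% | | |

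For a difference in means between two arms, the 95% half-width in SD units is t(0.975, 2n - 2) x sqrt(2/n). It is 0.75 at n = 15, 0.85 at n = 12, 1.00 at n = 9 and 1.29 at n = 6. Intervals of this width could hardly show whether the poorest families respond as the others do.

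**Step 4: what the plan already delivers.** Income category is collected (section 3.1.3) and falls within the demographics described by arm (section 6.4.1), so the enrolled mix will be visible. Section 6.3 allows further potential confounders into the model as needed, although that is a different purpose from a subset summary.

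**The case for a change.** The strongest reply is that site enrichment is presumed and not documented. No low-income share is given for the 3-4 practices, and a similar recruitment strategy need not mean the same sites or criteria. If about half the families were not low-income, the dilution would be 5 points at a gap of 10 and 10 points at a gap of 20 (0.50 x 10 and 0.50 x 20). A descriptive table and one sentence cost little, and the pilot label excuses the lack of a power calculation but not a mismatch between aim and sample.

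Part of this stands. Aim 2 does name low-income families, the body text has no income rule, and the share is unknown.

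The rest is weaker. The abstract and section 8.4.2 describe the next step as a larger and more diverse low-income population, which suggests that the investigators already regard the pilot population as low-income and that diversity is meant within it. The proposed table would be cut at poverty, which may not be Aim 2's population. Section 5.1.2 does not say whether income and education must both be met, and without the demographics form one cannot confirm that the income categories permit a cut at 100% of the Federal Poverty Level. The referral form is also not reproduced, so the absence of an income question at screening is established for the body text only.

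**Conclusion.** No change to the plan follows. The wording of Aim 2 is narrower than the eligibility rules, but the population is chosen through the setting, which is a fair trade-off in a pilot of 45 families sized on funds and time. Randomised comparisons between arms stay valid at any income mix, and no rule in section 6.4.3 gives a wrong answer.

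The possible distortion concerns how far the results carry over to low-income families. It is 1 to 4 points if 80% to 90% of families are low-income, and larger if the share is lower, with an assumed gap of 10 to 20 points. A below-poverty table would not settle this: it may describe a narrower group than Aim 2 names, with about 6 to 13 families per arm at assumed shares of 40% to 90%.

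Analysts can fill the gap sensibly in the report. They can show the income and maternal education mix with the baseline demographics, and word the conclusions for families attending the participating practices, extending them to low-income families as far as that mix supports it. A pooled summary in families below the threshold is at most an optional description. This conclusion rests on the setting enriching for low-income families, which the documents suggest but do not quantify.

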3 INVESTIGATIONAL PLAN

3.1 General Schema of Study Design

To be eligible to participate, children must be aged 6-24 months old, and have a parent with daily access to a smart phone in order to receive and send text messages. Inclusion and exclusion criteria for Phase 1 will be the same as Phase 2. In our previous study utilizing text messaging with low-income families for a study of early literacy promotion, only 28 (18.9%) of 148 eligible participants approached for recruitment were ineligible because they didn't have access to a smart phone. Children and their parents will be recruited from participating practices at any 6 through 24-month well child visit in which parents receive board books and reading promotion from their child's clinician as part of the ROR program.

3.1.1 Phase 1

Prior to conducting the RCT, we will develop the text messages and personalized coaching that we will employ in the RCT. The text messages were previously developed as part of the aforementioned trial on early literacy promotion (see appendix). Using a rapid-cycle design process developed by [name], data from brief interviews with N=10 parents will be used to identify specific behavioral barriers to more frequent reading with children, and to edit reminder messages and develop coaching content to target those barriers with behaviorally-informed solutions. Personalized coaching will consist of a menu of various instruction and tips on reading that participants can select based on their needs. The interviews will be audio recorded and transcribed in order to analyze content. In the event that the baseline visit cannot be completed in-person, an alternative method of obtaining informed consent will be used, and the interview will be completed over the phone. All interviews will be audiotaped and transcribed for analysis. Interview transcripts will be analyzed and coded using NVivo, a qualitative software. The information can inform the motivational tips in phase 2 to address barriers to shared reading.

Following the telephone screening, caregivers of eligible children will be sent the informed consent document electronically through REDCap. The study team will then go over the document in detail with the eligible caregiver by phone and use the e-consent function to obtain their signature. The signed e-consent form will be stored within REDCap and a copy will be made available to download and email securely to the caregiver.

3.1.2 Phase 2

After conducting the rapid-cycle design for phase 1, forty-five eligible children and their parents will be consented and enrolled in the study. In the event that the baseline visit cannot be completed in-person an alternative method of obtaining informed consent electronically through REDCap will be used. Following informed consent and completion of baseline surveys, participants will be stratified by site and randomized 1:1:1 to receive one of the 3 AH interventions for an 8-week duration. Using a similar recruitment strategy, we were able to successfully recruit 120 (81%) of 148 low-income infants and their parents who were approached for the aforementioned study on early literacy promotion.

Group 1 will consist of daily text messages on shared reading, which will be sent to participants using the Way to Health Platform. Participants will be asked to reply to the text message on daily shared reading activities including the titles of books and time spent reading. Group 2 will consist of Group 1 plus personalized coaching. Personalized coaching content will be made available to participants through links in the text messages and will provide comparisons of their reading frequency with that of other participants. These comparisons will be blinded to preserve confidentiality. Finally, Group 3 will consist of Group 2 plus availability of a weekly lottery. Group 3 participants who report back that they read on a particular day will be entered into a weekly drawing to receive \$20. Each reported daily reading behavior will provide a single lottery entry so that participants who report they read all 7 days in a given week will have 7 entries in the weekly drawing.

3.1.3 Randomized Trial

All participants across groups will be asked to report on daily reading behaviors by replying to daily text messages. In addition, participants will be asked to complete study measures using a RedCap survey at baseline and following the 8-week intervention period. Responses to daily reading text messages will be provided by the Way to Health platform and will be assessed as the mean overall number of days/weeks of reading for each group. Participants will also be provided with an opt out of the daily text messages option if they no longer desire to receive daily text messages. Participants will be queried at follow-up on their overall satisfaction (5-point Likert scale) with their intervention group and asked to answer survey questions regarding likes and dislikes concerning the intervention group they received following the intervention period. The survey questions at the end of phase 2 will be based on input from the rapid-cycle design process of phase 1 interviews.

At baseline, parents will complete a measure of demographics (child and parent age, race/ethnicity, sex, highest education completed, and family income category) (see Appendix 2). To explore differences in the home reading environment, parents will complete the Read subscale of the StimQ, a validated 14-item parent report measure of the home reading environment, at baseline and follow-up.²³ To explore differences in parenting stress, participants will complete the Parenting Stress Index-short form (PSI-SF), a validated 36-item parent report of parenting stress, at baseline and following the 8-week intervention in order to assess changes.²⁴ Finally to explore differences in child language and socio-emotional development, parents will complete at follow-up the MacArthur Communicative Development Inventory (CDI), a validated parent-report scale of early language development, and the Devereux Early

Childhood Assessment (DECA), a validated 33-item parent report of socio-emotional problems.^{25,26}

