6.3 Control of Bias and Confounding

Randomization and allocation concealment are the primary means of avoiding bias. Analytic strategies will also be used to control for residual confounding: (1) Stratification will control for imbalance not controlled by design. (2) Additional potential confounders will be evaluated for any residual association with treatment and included in model as needed. (3) Post randomization effects: The primary source of bias will arise after randomization from dropout and loss to follow-up. To address this problem and avoid missing data, we shall implement the following measures: (a) incentives to each family to complete the study, (b) collection of multiple contact numbers and tracking of changes, and (c) contact all randomized participants, even if they do not continue with their clinical contacts.

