6.4.3 Analysis of Primary Outcomes of Interest

6.4.3.1 Specific Aim 1

Primary outcomes:

To determine the feasibility of each group of the intervention, we will assess the proportion of participants who receive and report a daily reading behavior each week across all groups, the proportion of participants who access coaching content in group 2 & 3, and the proportion of participants who participate in the weekly lottery in group 3. To determine acceptability of the intervention, we will assess the number of participants who opt out of the daily text messages and query participants on their overall satisfaction (5-point Likert scale) with their intervention group and provide survey questions regarding likes and dislikes concerning the intervention group they received following the intervention period. The survey questions at the end of phase 2 will be based on input from the rapid-cycle design process of phase 1 interviews. Differences in weekly reading frequency and satisfaction scores between groups will be assessed using standard inferential statistics and intention-to-treat analysis. Survey question responses will be assessed using qualitative methods in which codes will be developed and emerging themes identified by consensus of investigators using NVivo software.

Secondary outcomes:

To explore differences in reading frequency, the home reading environment, parenting stress, and child language and socio-emotional development, we will examine differences in mean weekly reading frequency, mean changes in StimQ Read Subscale scores and PSI-SF scores, and mean CDI and DECA scores between groups using standard inferential statistics and intention-to-treat analysis. In addition, effect sizes will be computed to assess differences between Group 1 and each of the other 2 groups and to power future studies.

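### Reading frequency is defined only from text replies, so parents who opt out of the texts have no described outcome data for the intention-to-treat comparison

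*Combined protocol and SAP*

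**What the plan says.** Section 3.1.3 names one source for reading frequency: "All participants across groups will be asked to report on daily reading behaviors by replying to daily text messages". The replies come from the messaging platform and "will be assessed as the mean overall number of days/weeks of reading for each group". The same section adds: "Participants will also be provided with an opt out of the daily text messages option if they no longer desire to receive daily text messages".

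Section 6.4.3.1 uses reading frequency twice. Under the primary outcomes: "Differences in weekly reading frequency and satisfaction scores between groups will be assessed using standard inferential statistics and intention-to-treat analysis". Under the secondary outcomes: "we will examine differences in mean weekly reading frequency, mean changes in StimQ Read Subscale scores and PSI-SF scores". It also plans effect sizes for Group 1 against each other group, for use in powering later studies. For acceptability, "we will assess the number of participants who opt out of the daily text messages", so the plan itself expects that some parents may leave.

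Section 6.2 lists reading frequency among the secondary endpoints at 2 months. The measures listed for follow-up (Table 1 and sections 4.2.1 and 4.3) are StimQ-Read, PSI-SF, CDI, DECA, a satisfaction rating and a parent survey. None is described as measuring reading frequency.

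Section 6.3 names dropout and loss to follow-up as the main source of bias after randomisation. It answers with retention measures, among them a commitment to "contact all randomized participants, even if they do not continue with their clinical contacts". It gives no rule for unanswered texts or for days after opt-out.

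**The concern.** The daily text is both the intervention and the channel through which the outcome arrives. The plan does not say that opting out ends measurement. But a parent who receives no text has nothing to reply to, and no other source is named. An intention-to-treat comparison needs an outcome for everyone randomised. For this outcome, as written, there is none after opt-out.

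The analyst must then count the missing days as not read, leave the parent out, or average whatever was observed. These choices can give different answers from the same families. If opt-out differs between plain reminders, coaching and lottery, the reading comparison partly reflects who stayed subscribed. The comparison of Group 2 with Group 1 is exposed as well, although neither group is rewarded for replying. What is mainly at stake is the effect sizes meant to plan the next trial.

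**Working it through.** The plan gives no opt-out rate, mean, SD or stated result for this outcome, so there is no figure to reproduce. From the plan: 15 parents per arm (section 6.4.2) and 8 weeks of daily texts (section 1.2). Everything else below is assumed.

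**1. Later days counted as not read, true reading equal in both arms.** With true mean μ, k opt-outs of 15, and opt-out after week w:

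observed mean = μ × [1 − (k/15) × (8 − w)/8]

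- μ = 4, k = 3, w = 2: 4 × [1 − 0.20 × 0.75] = 3.40. Check by parents: (12×4 + 3×4×2/8)/15 = 51/15 = 3.40.
- The other arm, with no opt-outs, shows 4.00. The false gap is 0.60 days/week, or 0.60/2 = 0.30 SD at an assumed SD of 2.

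The gap between two arms is μ × (difference in opt-outs/15) × (8 − w)/8. I varied μ from 3 to 5, opt-outs over 2 v 0, 3 v 1, 4 v 1 and 5 v 1, and w over 2 and 4:
- smallest: 3 × 2/15 × 4/8 = 0.2 days/week (0.10 SD)
- largest: 5 × 4/15 × 6/8 = 1.0 days/week (0.50 SD)

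**2. One arm, leavers read less.** Twelve parents read 4 days/week. Three read 2 days/week throughout and opt out after week 2. The true mean is (12×4 + 3×2)/15 = 54/15 = 3.60.

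| Handling of days after opt-out | Calculation | Mean | Error |
|---|---|---|---|
| Counted as not read | (48 + 3×2×2/8)/15 = 49.5/15 | 3.30 | −0.30 |
| Opted-out parents excluded | 48/12 | 4.00 | +0.40 |
| Observed weeks pooled over parents | (12×8×4 + 3×2×2)/(96 + 6) = 396/102 | 3.88 | +0.28 |
| Each parent's observed weeks averaged, then averaged over parents | (12×4 + 3×2)/15 | 3.60 | 0 |

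The last row is unbiased here because each parent's reading is constant over time. It would not be if reading changed after opt-out.

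**3. Simulation with no true difference.** 15 per arm, reading drawn with mean 4 and SD 2 (limited to 0–7), 4 opt-outs in one arm and 1 in the other after week 2, two-sided t-test at 0.05, 6,000 runs. The difference shown is for the arm with more opt-outs.

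| Who leaves | Rule | Mean difference, days/week | Rejection rate |
|---|---|---|---|
| Lowest readers | Counted as not read | −0.31 | 2.8% |
| Lowest readers | Excluded | +0.57 | 17.2% |
| Unrelated to reading | Counted as not read | −0.58 | 8.1% |
| Unrelated to reading | Excluded | about 0 | 5.0% |

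Having exactly the lowest readers leave is an extreme case. Size and sign both turn on the handling rule and on who leaves.

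**The case against.** **The missing item may exist.** A reader might infer that opted-out parents are never asked how often they read. The documents do not support that. The parent questionnaire, the StimQ-Read items and the appendices are not shown, and the survey is to be built from Phase 1 interviews about barriers to reading. What can be said is that no such measure is described: sections 3.1.3 and 6.4.3.1 present the survey as covering likes and dislikes, and list StimQ-Read under the home reading environment, apart from reading frequency.

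**Dropping silent days need not bias.** A reader might take the pooled 3.88 as the error from leaving those days out. The plan does not prescribe pooling over weeks. With the parent as the unit, the same data give 3.60, which is the true value. Exclusion biases the mean only if leaving is related to reading.

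**Differing opt-out is assumed.** This stands. No figure in the plan shows that the arms will differ, which is why a range is given.

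**It is a pilot, and engagement is reported anyway.** The primary aim is feasibility and acceptability, reading differences are exploratory under Aim 2, and opt-outs and weekly reporting will be shown. This limits the harm. It does not remove it, because section 6.4.3.1 also tests weekly reading under the primary outcomes and carries effect sizes forward.

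**A recall item answers a different question.** This also stands in part. Texts end at week 8, while follow-up may fall at weeks 8–12 (Table 1; section 3.3.1). An item on the past 7 days could therefore describe a week up to four weeks after the intervention. It should be anchored to the intervention and should not replace the daily reports.

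**Conclusion.** The point holds in a limited form and should be addressed. As described, reading frequency has no source for parents who have opted out, and the plan has no rule for their silent days, yet it promises an intention-to-treat comparison and effect sizes for later trials.

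If opt-out differs by arm, counting later days as not read creates a false difference of 0.60 days/week in the main example and about 0.2 to 1.0 over the inputs tried. Excluding opted-out parents overstates the mean when low readers leave (4.00 against a true 3.60). Averaging each parent's observed weeks need not bias it. All of these sizes rest on assumed reading levels, opt-out counts and timing.

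It would go too far to infer that the reading comparison is certain to be biased, or that the other outcomes share the problem. StimQ-Read, PSI-SF, CDI and DECA are collected by survey and do not depend on staying subscribed to the texts.

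**What to change.** 1. Unless the questionnaire already contains one, add a single item to the baseline and follow-up REDCap surveys asking on how many days of a 7-day period the parent read with the child. At follow-up, anchor it to the last week of the 8-week intervention. Ask it of every randomised parent, including those who opted out of texts. If such an item already exists, name it in section 6.4.3.1 and anchor it in the same way.
2. Report an intention-to-treat comparison of this item alongside the text-based mean, and use it when deriving effect sizes for future trials.
3. For the text-based mean, state that the parent is the unit. Show each scheduled day as read, not read, no reply or opted out. Present the mean twice: with silent days counted as not read, and with them treated as missing.

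The cost is one question at two existing contacts and a few sentences in the analysis section. Section 6.3 already commits to contacting everyone randomised. The downside is that recall is coarser than daily reports and covers one week only. When follow-up is late, the parent must also recall a week that ended up to four weeks before.
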